## OVERVIEW OF STUDY PROTOCOL

Title of Study:	A Prospective, Multi-center, Single Arm Study to Evaluate the Safety and Effectiveness of the CODMAN ENTERPRISE® Vascular Reconstruction Device and Delivery System when Used in Conjunction with Endovascular Coil Embolization in the Treatment of Wide-necked Saccular Intracranial Aneurysms
Study Devices:	CODMAN ENTERPRISE® Vascular Reconstruction Device and Delivery System (CODMAN ENTERPRISE) and CODMAN ENTERPRISE® 2 Vascular Reconstruction Device (ENTERPRISE 2), hereafter referred to as ENTERPRISE.
Comparator Device:	This is a single arm study with no comparator device.
Study Sponsor:	Cerenovus [name]
Study Objectives:	
The primary objectives of the study are to evaluate the safety (as assessed by rates of major ipsilateral stroke and/or death and in-stent stenosis) and effectiveness (as assessed by the rate of complete angiographic occlusion) of ENTERPRISE when used in conjunction with endovascular coil embolization of unruptured wide-neck intracranial saccular anterior circulation aneurysms in a prospective, multi-center, single-arm clinical study.
 
Secondary effectiveness objectives include the evaluation of treatment outcomes for subjects treated with ENTERPRISE in the acute (procedure and immediate post-procedure time frames) and follow-up phases of patient management.
 
Secondary safety objectives include the evaluation of adverse safety outcomes for subjects treated with ENTERPRISE from the start of the procedure through the end of study participation (12 months or premature discontinuation of study participation).

In addition, the rates of stent movement and migration in ENTERPRISE-treated subjects will be described.

**Study Design:**

This is a prospective, multi-center, single arm, clinical study to evaluate the safety and effectiveness of the ENTERPRISE stent when used in conjunction with endovascular coil embolization in the treatment of unruptured wide-neck, intracranial, saccular anterior circulation aneurysms ( $\leq 10$  mm) arising from a parent vessel with a diameter of  $\geq 2.5$  mm and  $\leq 4$  mm. A group sequential design will be utilized in which one primary endpoint interim analysis will be conducted after  $N=160$  subjects have been enrolled and followed through 6 months post-procedure, to determine if the study should stop early for futility or a tentative determination of success; enrollment will pause after these 160 subjects have been enrolled. If the stopping rule is met for the trial to stop early for tentative success, a final confirmatory analysis will be conducted when all subjects have reached 12 months post-procedure. If the trial is not terminated early for futility or tentative success, then enrollment will continue up to a full enrollment sample size of  $N=320$ , and a final analysis will be conducted when all subjects have reached 12 months post-procedure.

An analysis will be conducted to support a marketing application after all subjects have reached 12 months post-procedure. The remaining data out to 24 months post-procedure will be submitted as a post-approval study (PAS) report once all subjects have completed their 24 month follow-up.

**Sample Size:**

A group sequential design will be utilized in which  $N=160$  subjects are enrolled and followed for a minimum of 6 months post-procedure, at which time an interim analysis will be conducted to determine whether or not to terminate the study early for futility or a tentative determination of success. If the trial is not terminated early for futility or tentative success, then enrollment will resume to a maximum enrolled sample size of  $N=320$  (including the original  $N=160$ ). Subjects who are enrolled but who are found to be ineligible for treatment with ENTERPRISE at the time of the pre-procedure angiogram will be replaced. Subjects in whom treatment with ENTERPRISE is

attempted but who discontinue study participation prematurely will not be replaced.

**Number of Sites:** Up to 25 institutions in the United States

**Study Population:** Subjects with an unruptured wide-neck, intracranial saccular anterior circulation aneurysm ( $\leq 10$  mm), arising from a parent vessel with a diameter of  $\geq 2.5$  mm and  $\leq 4$  mm, will be eligible for the study. Wide-necked is defined as having a neck width  $\geq 4$  mm or a dome-to-neck ratio  $< 2$ . Only one wide-necked aneurysm will be treated for each subject during the index procedure.

**Study Procedures:** The study evaluation time points include:

1. Screening/Baseline
2. Procedure/Treatment Period
3. Hospital Discharge
4. Thirty Day Follow-up (Telephone Interview)
5. 6 Month Follow-up (Clinic Visit & Angiogram)
6. 12 Month Follow-up (Clinic Visit & Angiogram),
7. 18 Month Follow-up (Telephone Interview)
8. 24 Month Follow-up (Clinic Visit plus MRA or angiogram)

**Primary Effectiveness Endpoint:** **Rate of Complete Aneurysm Occlusion (RCAO) according to the Raymond Scale:**

The primary effectiveness endpoint is the rate of complete aneurysm occlusion (RCAO) at 12 months post-procedure according to the Raymond Scale as assessed by the Independent Core Laboratory. Complete aneurysm occlusion is defined as an aneurysm in which a score of 1 (complete obliteration) is achieved on the Raymond Scale at the relevant post-procedure angiogram, without additional procedures for treatment of the aneurysm since the index procedure. Subjects who are retreated (retreatment includes staged procedures) prior to the 12 month post-procedure follow-up visit will be considered not to have achieved complete aneurysm occlusion for the purpose of the primary endpoint analysis.

The primary endpoint analysis will be to demonstrate that the RCAO is significantly greater than a performance goal

(PG) of 35%. The primary endpoint null and alternative hypotheses are:

Null hypothesis  $H_0$ :  $RCAO \leq 35\%$

Alternative hypothesis  $H_A$ :  $RCAO > 35\%$

This analysis will be conducted on the modified intent-to-treat (MITT) population of subjects (subjects who are found to be eligible for treatment with ENTEPRISE at the time of the pre-procedure angiographic assessment, and in whom treatment is attempted). A supportive analysis will be conducted on the PP population.

**Note:** The study will be deemed to be a success if this primary efficacy endpoint null hypothesis (on the MITT population with data from all sites combined) is rejected in favor of the alternative hypothesis.

**Primary Safety Endpoints:**

There are two primary safety endpoints: Major Ipsilateral Stroke and/or Death at 12 months post-procedure and In-stenosis at 12 months post-procedure.

The analyses of these safety endpoints will be conducted on the MITT population. Supportive analyses will be conducted on the PP population.

**Incidence of Major Ipsilateral Stroke and/or Death:**

The incidence of a major ipsilateral stroke and/or death will be evaluated from the start of the index procedure until completion of the 12 month follow-up. A major ipsilateral stroke is defined as a new neurological event which is ipsilateral and in the vascular distribution territory of the stenting procedure and that results in an increase of  $\geq 4$  on the National Institute of Health Stroke Scale (NIHSS) as compared to baseline and persists for greater than 24 hours.

For a successful evaluation of this endpoint, the upper confidence limit of a 2-sided 95% confidence interval for the proportion of subjects who experience major ipsilateral stroke and/or death through 12 months post-procedure will be less than 25%.

**Incidence of In-stent Stenosis:**

The percentage of stents in which stenosis is assessed angiographically, at or prior to 12 months post-procedure will be evaluated. Stenosis is defined as greater than 50% narrowing of the vessel within the ENTERPRISE stent or within 10 mm of either end of the stent (i.e., in-stent stenosis).

For a successful evaluation of this endpoint, the upper confidence limit of a 2-sided 95% confidence interval for the rate of in-stent stenosis at or prior to 12 months post-procedure will be less than 15%.

**Secondary Effectiveness Endpoints:**

The following secondary effectiveness endpoints have been defined. Observed rates will be described for both the MITT and PP populations. All angiographic imaging results will be based upon assessments by the independent Core Laboratory. A subject who is retreated (retreatment includes staged procedures) is considered to be a treatment failure for endpoints based on angiographic imaging.

**a) Procedure Success Rate:**

The procedure success rate is defined to be the percentage of aneurysms in which coil mass position is maintained within the sac with parent artery patency, without additional procedures for treatment of the aneurysm since the index procedure. The procedure success rate will be summarized immediately post-treatment (acute), and at the 6 and 12 month follow-up assessments.

**b) Complete Aneurysm Occlusion as per the Raymond Scale:**

The percentage of aneurysms in which a score of 1 (complete obliteration) is achieved on the Raymond Scale immediately post-procedure (acute) and at the 6 and 12 month follow-up angiographic assessments, respectively, will be evaluated.

**c) Complete/Partial Aneurysm Occlusion as per the Raymond Scale:**

The percentage of aneurysms in which a score of 1 (complete obliteration) or 2 (residual neck) is achieved

on the Raymond Scale immediately post-procedure (acute), and at the 6 and 12 month follow-up angiographic assessments will be evaluated.

**d) Percent Aneurysm Occlusion:**

The percentage of aneurysms with occlusion of 100%, 90%-99%, 70-89%, 50-69%, 25-49%, or <25% occlusion in accordance with Consensus Grades 0-5, respectively, will be summarized immediately post-procedure (acute), and at the 6 and 12 month follow-up, respectively.

**e) Recanalization Rate:**

The percentage of aneurysms in which recanalization is documented at any time up to and including the 12 month follow-up visit, will be evaluated. Recanalization will be defined as an increase in aneurysm filling as compared to the previous study-specified angiographic assessment, resulting in a change in (i.e., worsening of) the Raymond classification. Changes in Raymond Scale will be classified as stable, improved, or recanalized based on the follow-up angiograms. Percentages of aneurysms falling into each of the categories will be presented.

**f) Retreatment Rate:**

The percentage of target aneurysms that are retreated at any time up to and including the 12 month follow-up visit will be evaluated. Retreatment will be defined as any additional treatment of the target aneurysm after the index procedure (retreatment includes staged procedures), or an additional procedure (regardless of whether retreatment is by surgery or endovascular treatment) due to recanalization, rupture or bleeding.

**Secondary Safety Endpoints:**

The evaluation of the rate of new neurological deficits (increase in mRS > 2 from baseline not related to stroke or death) at 12 months will be a pre-specified, powered analysis. All other secondary endpoints will be presented as a group to better characterize the ENTERPRISE stenting procedure.

Unless otherwise stated, these secondary safety analyses will be conducted on the MITT population.

**a) Rate of New Neurological Deficits per the Modified Rankin Scale (mRS):**

Observed scores on the Modified Rankin Scale will be presented at baseline (pre-procedure) and follow-up (30 days, 6 and 12 months post-procedure). The number and percentage of subjects who have an increase in mRS > 2 from baseline not related to stroke or death will also be presented for each follow-up time point.

The evaluation of the rate of new neurological deficits at 12 months post-procedure will be a pre-specified, powered analysis. For a successful evaluation of this endpoint, the upper confidence limit of a 2-sided 95% confidence interval for the rate of subjects with a new neurological deficit will be less than 15%. The analysis of new neurological deficits will exclude subjects who had a stroke or who died from the time of the index procedure to the time of the evaluation.

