### **United States Data**

The US clinical study includes data on subjects enrolled between 22 June 2004 and 12 October 2004. Subjects were followed for six months. The database was closed on 13 July 2005.

Baseline data were presented on 30 subjects who enrolled into the study and on 28 subjects who received the CODMAN ENTERPRISE stent and followed through six months. Two subjects were enrolled into the study but did not receive the device due to pre-procedure angiographic disqualification. In one case, the parent vessel was too large in diameter

and in the other, the aneurysm neck was too wide. The majority (76.7%) of the subjects was female, and the average age was 57.8 years. A medical history of hypertension was reported in 66.7% of the subjects enrolled and 40.0% had cardiovascular disease. The most commonly reported neurological event was pounding/pulsatile headache (43.3%) and 26.7% had a history of Altered Mental Status. Five subjects (16.7%) had previously suffered a subarachnoid hemorrhage, and 23.3% of the subjects had undergone a prior intracranial embolization procedure for their cerebral aneurysm.

All serious adverse events were reviewed and adjudicated by the Clinical Events Committee. Seven subjects (25%) experienced one or more device or procedure related serious adverse events. One subject died as a result of an intracerebral hemorrhage post-operatively. This death was classified as secondary to the presenting intracerebral hemorrhage. Eighteen subjects experienced 47 other adverse events that were judged to be at least possibly related to the device or procedure. The majority of these events occurred within 30 days.

Neurological assessments included NIH Stroke score, modified Rankin score and clinical neurological examination. Most subjects experienced no change or improved neurological assessment ratings from pre-procedure to six months.

The mean NIH Stroke score was 1.4 pre-procedure and was 0.3 at six months. This indicates that there was benefit for both neurological and overall clinical improvement following treatment, since an NIH stroke scale core of "0" is an indication of being completely normal. The majority of subjects (75.9%) were rated Grade 0 or Grade 1 on the modified Rankin scale pre-procedure, and 80.7% of subjects were Grade 0 or Grade 1 at six months (a Rankin scale of "0" indicates no neurological disability).

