### **9.3 Levels of Significance**

A 2-sided alpha of 0.05 will be used for statistical testing and confidence intervals unless otherwise noted. There will be no adjustment to p-values or alpha levels for testing primary safety, secondary effectiveness, or secondary safety endpoints.

A primary efficacy endpoint interim analysis will be conducted to determine whether or not to stop the trial early for futility or tentative success. This analysis will be based solely on the primary efficacy endpoint, and will be conducted after N=160 subjects have been enrolled and have reached 6 months post-procedure. In this interim analysis, the two-sided unadjusted p-value threshold for stopping the trial early for success will be 0.031. If the stopping rule is met for the trial to stop early for tentative success, a final confirmatory analysis will be conducted when all subjects have reached 12 months post-procedure; a p-value threshold of 0.031 will be used for this final confirmatory analysis. If this early stopping rule is not met, then enrollment will commence until the total sample of N=320 subjects have been enrolled (including the original N=160). The final endpoint analysis with all be conducted with a 2-sided p-value threshold of 0.031 for determining study success. These p-value thresholds have been established in order to maintain an overall 2-side alpha (probability of a Type 1 error) below 0.05 for the primary endpoint.

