## 9.5 Handling of Missing Data

Primary effectiveness and primary safety endpoint analyses will be conducted on the modified intent-to-treat (MITT) population, where subjects with missing data at the time of endpoint analysis will be imputed as last observation carried forward (LOCF); see Section 9.8 for analysis set definitions. Note that the immediate post-procedure evaluation will be utilized in this LOCF methodology if this is the last observation on file. MITT subjects who receive the device but in whom there is no post-procedure data will be treated as failures for the purpose of the primary effectiveness endpoint analysis; these subjects will be excluded from all other endpoint analyses. Subjects who do not receive the device because of treatment failure due to reasons associated with the device will also be treated as failures for the primary effectiveness endpoint analysis; these subjects will be excluded from all other endpoint analyses. MITT subjects who do not receive the device because of an intra-operative surgeon decision based on patient anatomy (e.g. vessel tortuosity) will be treated as missing (and not as failures) in all endpoint analyses, including the primary effectiveness and primary safety endpoint analysis.

All subjects who have died prior to an evaluation will have a mRS score of 6 imputed for that time point for analysis purposes.

All other analyses based upon MITT or PP population data will be based upon actual data, with no data imputation.

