10.4.2.2 Secondary Safety Endpoints

- Rate of new neurological deficits as per mRS

The number and percentage of subjects with new neurological deficits, not related to stroke or death, will be summarized at baseline (pre-procedure) and follow-up visits, e.g., 30 days, 6 and 12 months post-procedure. Subjects who died prior to an evaluation will have an mRS score of 6 imputed at that timepoint for analysis purpose.

- NIHSS total score

The NIHSS total score and its change from baseline will be summarized at baseline (pre-procedure) and follow-up visits (6 months and 12 months post-procedure). In addition, the number and percentage of subjects who show a worsening from baseline (an increase of 4 points or more) will also be presented. Only the observed scores will be included in summaries.

- Adverse Events and Clinical Complications

AEs from the start of the index procedure until completion of the 12-Month Follow-up will be coded using the latest version of Medical Dictionary for Regulatory Activities (MedDRA) into system organ class (SOC) and preferred terms (PTs). The number of events, the number and percentage of subjects with events and event rates by SOC and PT will be summarized for the following:

- Any AEs
- Study device or procedure related AEs
- Any serious AEs (SAEs)
- Unanticipated AEs
- AEs leading to death

AEs related to device/procedure are defined as those with the relationship of definitely, probably or possibility related. AEs with miss relationship will not be imputed. Subjects with multiple relationships on the same AE will be reported by the events of the highest relationship. Only the relationship as determined by CEC will be used in the safety analysis.

In addition, device or procedure related AEs will be presented overall and by study period as follows:

Table 2: AEs by Study Period

Study Period	Lower Bound of AE Start Date	Upper bound of AE Start Date
Peri-procedure	from the beginning of the procedure	Until 24 hours post-procedure (Day 0)
12-Month Follow-up	After 24 hours post-procedure (i.e., from Day 1)	Until the date of: 
○ early discontinuation in the study; or

Study Period	Lower Bound of AE Start Date	Upper bound of AE Start Date
		
 ○ the upper bound of the 12-Month analysis window (i.e., Day 450)

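### Under the protocol's definition, subjects with baseline mRS 3 or higher cannot have a new neurological deficit, yet they stay in the denominator and lower the reported rate by an unknown, possibly negligible, amount

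*Protocol*

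**What the plan says.** The protocol Overview (Secondary Safety Endpoints, item a) counts "subjects who have an increase in mRS > 2 from baseline not related to stroke or death" at each follow-up. Sections 3.2.4.1 and 9.6 repeat the definition. The 12-month rate is singled out as the one prespecified, powered secondary safety analysis. Its goal is that the upper limit of a 2-sided 95% interval for "the rate of subjects with a new neurological deficit will be less than 15"%.

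On the denominator, the Overview says that, unless otherwise stated, "these secondary safety analyses will be conducted on the MITT population", and it gives one restriction: "The analysis of new neurological deficits will exclude subjects who had a stroke or who died from the time of the index procedure" up to the evaluation. Nothing is said about baseline mRS. On the scale, protocol 9.5 says: "All subjects who have died prior to an evaluation will have a mRS score of 6 imputed".

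The eligibility criteria (4.1.1 to 4.1.4) contain no mRS limit. The nearest rule excludes a Barthel Index below 80, but only when the cause is something other than the index aneurysm.

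SAP 10.4.2.2 summarises "The number and percentage of subjects with new neurological deficits, not related to stroke or death", with no point threshold and no baseline restriction. SAP sections 6 and 10.1 withdraw hypothesis testing because the study was stopped early, and SAP 10.1 bases percentages on non-missing values.

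**The concern.** A rate is interpretable when everyone in the denominator could have been in the numerator. Here the combination of a 3-point rise and the removal of death puts a ceiling on the scale. Subjects who begin with moderate or worse disability can only ever add to the denominator. The bias has one direction: the rate looks lower than it is among those who could have the event.

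This is also the only secondary safety endpoint for which the protocol sets a numerical goal. A shift from mRS 3 to mRS 5 would be a serious deterioration, but it would enter the table as no new deficit.

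**Working it through.** **Inputs**

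- Event: rise of more than 2, so at least 3 whole points (protocol Overview, 3.2.4.1, 9.6).
- Top of scale: 6 is death (protocol 9.5), so 5 is the highest score of a living subject.
- Removed from the analysis: stroke and death only (protocol Overview).
- Goal: upper 2-sided 95% limit below 15% (protocol Overview). The default level is set in protocol 9.3: "A 2-sided alpha of 0.05 will be used for statistical testing and confidence intervals unless otherwise noted".
- Share f with baseline mRS 3 or higher: not given. The nearest figures are in protocol 1.3.1. For the US feasibility study, "The majority of subjects (75.9%) were rated Grade 0 or Grade 1 on the modified Rankin scale pre-procedure", so 100 − 75.9 = 24.1% were at 2 or higher. The European study reports 96.8% at 0 or 1, so 3.2% were at 2 or higher. Both are shares at 2 or higher, and a subject at 2 can still be an event, so they are only upper bounds on f in those cohorts.
- Sample size: the protocol states no N, expected rate or power for this endpoint. N = 150 is borrowed from the primary safety endpoints.

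**Is the borrowed N used consistently in the plan?** With power = Φ{[|p0 − p1| − 1.96·√(p0(1−p0)/n)] / √(p1(1−p1)/n)} and n = 150, stenosis (15% vs 6%) gives 95.49% against the stated 95.5%. Stroke/death (25% vs 14%) gives 92.46% against 92.5%. Both reproduce. There is no corresponding figure to reproduce for the new-deficit endpoint.

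**Step 1: the ceiling.** Largest rise without death = 5 − baseline mRS.

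| Baseline mRS | Largest rise | Can be an event? |
|---|---|---|
| 0 | 5 | yes |
| 1 | 4 | yes |
| 2 | 3 | yes, only by reaching 5 |
| 3 | 2 | no |
| 4 | 1 | no |
| 5 | 0 | no |

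**Step 2: dilution.** Reported rate = r × (1 − f), with r the rate among subjects at baseline 0–2. For r = 15%: 0.15 × 0.968 = 14.5%; 0.15 × 0.90 = 13.5%; 0.15 × 0.759 = 11.4%.

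**Step 3: effect on the protocol's planned criterion only.** Upper limit = p + 1.96·√(p(1−p)/n). At n = 150 the rule passes with up to 15 events (10.0%, limit 14.80%); 16 events give 15.6% and fail. The table places the same 15 events on the at-risk denominator. It also gives the binomial chance of passing when r is exactly 15%.

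| f (assumed) | At-risk n | 15% reads | Limit for 15 events, at-risk n | Chance of passing, all subjects | Chance of passing, at-risk n |
|---|---|---|---|---|---|
| 0 | 150 | 15.0% | 14.8% | 4.9% | 4.9% |
| 1% | 148 | 14.85% | just under 15.0% | 5.6% | 5.6% |
| 3.2% | 145 | 14.5% | 15.3% | 6.8% | 4.0% |
| 10% | 135 | 13.5% | 16.4% | 12.4% | 4.6% |
| 24.1% | 114 | 11.4% | 19.4% | 34.7% | 3.5% |

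**Step 4: sensitivity to N.** If 14% were removed for stroke or death, n = 150 × 0.86 = 129 and the rule allows 12 events. Those 12 events still pass on the at-risk denominator at f = 3.2% (n = 125, limit 14.8%) and fail at f = 10% (n = 116, limit 15.9%).

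**The case against.** The case for leaving this alone is substantial, and most of it stands.

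- **The test is gone.** The SAP cancels inference and analyses whatever enrolment was achieved. The chances of passing in Step 3 therefore describe a decision that will not be taken. A reader might infer from them that the trial could wrongly declare neurological safety; under the current plan it cannot.
- **The size is unknown.** The feasibility cohorts included subjects with hemorrhage histories (38.7% in Europe, 16.7% in the US), and 3.2% of 31 is one subject. This trial requires an unruptured, previously untreated target aneurysm. It also excludes dementia, stroke or TIA in the last 6 months, and most causes of a low Barthel Index. Nothing supports 10% or 24.1% here, and at 1% the pass boundary does not move.
- **A rate of 15% is the null boundary.** If the 6% expected for stenosis is borrowed as an assumption, dilution gives 0.06 × 0.968 = 5.8% and 0.06 × 0.90 = 5.4%, which are small shifts.
- **The ceiling is not in the SAP's words.** The SAP gives no threshold, so the ceiling follows from the protocol definition that the SAP presumably inherits.
- **Worsening is not invisible.** The protocol presents mRS scores by visit, and both documents report NIHSS worsening of 4 or more points and adverse events, whatever the baseline mRS.

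Two things survive. Separate visit distributions do not pair a subject's baseline with the follow-up score, so a move from 3 to 5 can be missed on the mRS. And no text removes subjects who cannot have the event from the denominator.

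**Conclusion.** The structural flaw is certain on the protocol's definition: a subject starting at mRS 3–5 cannot be an event and counts as free of deficit, so the rate is understated by the factor (1 − f). Its size cannot be established. Under assumed shares, a true 15% would read 14.5% at f = 3.2% and 13.5% at f = 10%; at f near zero nothing changes.

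This rests on reading the definition as a change of more than 2 points, on the SAP intending that same definition, and on f, which the documents do not give. Any statement about meeting the 15% goal also rests on the borrowed N = 150 and applies only to the protocol's planned test.

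A reader might conclude that the device will look neurologically safer than it is. The documents do not support that as a fact: they show the direction of a possible bias, and it may be zero. Severity: minor, a matter of making a descriptive safety table interpretable.

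**What to change.** In SAP 10.4.2.2, under the mRS endpoint:

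1. State the protocol's threshold of a rise of more than 2 points.
2. Report the rate among subjects with baseline mRS 0–2, alongside the all-subject rate if wished.
3. State how many subjects start at mRS 3 or higher.
4. Add a baseline-by-12-month mRS shift table for all subjects, so that worsening from 3, 4 or 5 can be seen.

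Protocol Table 1 already schedules mRS at baseline and at 12 months, so no new data are needed. The cost is a slightly smaller denominator, hence a slightly less favourable and slightly less precise rate, plus one table. If no subject starts at 3 or higher, the two rates coincide and the table shows that the concern is empty.
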